3. OBJECTIVES AND ENDPOINTS

Objectives	Endpoints
Primary	
To determine the efficacy of cusatuzumab in combination with azacitidine in patients with previously untreated AML who are not eligible for intensive chemotherapy	Complete response (CR) rate per ELN 2017 (Dohner 2017) ⁶
Secondary	

To determine other response measures (see definitions in Table 6)
 
To assess time to response and duration of response
 
To determine transfusion independence
 
To assess the safety profile of cusatuzumab in combination with azacitidine
 
To assess the pharmacokinetics of cusatuzumab alone and in combination with azacitidine
	
 • Rate of CRh • Rate of CR + CRh • Rate of CRi • Overall response rate (ORR) = Rate of CR+ CRh+ CRi • Rate of CR without MRD • Rate of MRD negativity among participants achieving CR, CRh, CRi, or MLFS; defined as less than 1 blast or leukemic stem cell in 1,000 leukocytes (MRD level $<10^{-3}$) 
Time to response, defined as time from randomization in Part 1 or enrollment in Part 2 to achieving the first response of CR, CRh, or CRi; duration of response, defined as time from achieving the first response of CR, CRh, or CRi to disease relapse or death from any cause.
 
Transfusion independence (RBC or platelets) is defined as a period of at least 56 consecutive days with no transfusion between first dose of study drug and the last dose of study drug + 30 days.
 
Safety profile of Adverse Events (AE) and Serious Adverse Events (SAE)
 
Pharmacokinetics

Objectives	Endpoints
To assess the immunogenicity of cusatuzumab alone and in combination with azacitidine	Immunogenicity / anti-drug antibody testing
Exploratory	
To assess progression-free survival (PFS)	PFS is defined as the time from randomization in Part 1 or enrollment in Part 2 to progressive disease, relapse from CR/CRh/CRi, or death from any cause, whichever occurs first.
To assess overall survival (OS)	OS is defined as the time from randomization in Part 1 or enrollment in Part 2 to death
To assess pharmacodynamics and to explore biomarkers predictive of clinical response	Exploratory biomarkers including baseline level of CD70+ blasts, CD70+LSC, sCD27, NK cells
To assess patient-reported symptom severity and health-related quality of life	PROs using the FACT-Leu and EQ 5D 5L (See Section 10.8 Appendix 8 and Section 10.9 Appendix 9)
To collect medical resource utilization (MRU) data that may be used in future economic modeling (the construction and reporting of the economic model will be conducted separately from this study).	Duration of hospitalization (total days length of stay, including duration by wards; eg, intensive care unit) Outpatient medical encounters and treatments (including physician or emergency room visits, selected tests and procedures, and medications)

HYPOTHESIS

The primary hypothesis of this study is that the combination of cusatuzumab at doses of 10 mg/kg or 20 mg/kg with azacitidine has a CR rate of no less than 35% in patients with previously untreated AML who are not eligible for intensive chemotherapy.

4. STUDY DESIGN

4.1. Overall Design

This is an open-label study. The study will consist of 2 sequential parts, Part 1 and Part 2, as described below. The purpose of Part 1 is to select a dose schedule based on the totality of the data, including CR rate and other efficacy endpoints, PK, biomarkers, and safety. The purpose of Part 2 is to further evaluate and confirm the efficacy and safety of the combination therapy at the selected dose of cusatuzumab.

NOTE: Part 2 of the study will not be conducted because further development of this regimen (cusatuzumab in combination with azacitidine) in patients with unfit AML will not be pursued due to the evolving treatment landscape in AML.

NOTE: After 22 Oct 2021, ongoing subjects (on treatment or in follow-up) will be treated and assessed according to a reduced schedule of assessment (Table 1A).

Part 1 of the study is a randomized study of 2 doses of cusatuzumab in combination with azacitidine in patients with previously untreated AML who are not eligible for intensive chemotherapy. Part 2 of the study is an expansion of the selected dose. The study will include a Screening Phase, a Treatment Phase, and a Follow-up Phase. The Screening Phase will be up to 28 days prior to randomization. The Treatment Phase will extend from Cycle 1/ Day 1 until study intervention discontinuation. Participants will be treated with their assigned dosing regimen until disease progression, relapse, unacceptable toxicity, or withdrawal due to investigator discretion or withdrawal of consent. The Follow-up Phase will begin once a participant discontinues study intervention, and will continue until death, loss to follow up, consent withdrawal for study participation, or study end, whichever occurs first. Safety and efficacy data will be closely monitored on an ongoing basis by the Sponsor's central clinical team.

Part 1:

During Part 1, participants will be stratified by type of AML (de novo versus secondary AML) and ECOG score (0-1 versus 2) and then assigned randomly in a 1:1 ratio to receive cusatuzumab and azacitidine according to 1 of the following 2 dosing regimen groups:

- Group A: Azacitidine 75 mg/m² SC or IV on Day 1 through Day 7, cusatuzumab 10 mg/kg IV on Day 3 and Day 17 of each 28-day cycle
- Group B: Azacitidine 75 mg/m² SC or IV on Day 1 through Day 7, cusatuzumab 20 mg/kg IV on Day 3 and Day 17 of each 28-day cycle

Part 1 of the study utilizes a 3-stage monitoring approach as the statistical guidance to select a dose schedule (see Section 9.5, Interim Analysis). The cumulative number of participants for each dose group at each of the 3 stages are 15, 30, and 50, respectively. Response will be based on all evaluations up to the time point when the last participant is treated for a minimum of 3 cycles with combination therapy (cusatuzumab + azacitidine). At each stage, available data of efficacy, safety, pharmacodynamics, and biomarkers will be evaluated by a Data Review Committee (DRC) to determine if either or both of these treatment groups should continue into the next stage of Part 1, and by the end of Part 1 (n=50/group), to select 1 dose schedule to be continued into study Part 2. The DRC will be formed prior to the first participant being enrolled in the trial and will remain in place until the conclusion of the trial. Enrollment does not pause at each stage. Refer to Committees Structure in Appendix 3 (Section 10.3), Regulatory, Ethical, and Study Oversight Considerations for details.

If, based upon the totality of the data, 1 treatment group is considered to be less effective at any stage of Part 1, then that treatment group will be closed to enrollment. Upon 1 dose level being selected to continue, the DRC may determine to switch ongoing participants to treatment with the dose level selected. If 1 dose group is determined at Stage 1 or Stage 2 not to continue, the other dose group will be continued into study Part 2 directly without further evaluations in Part 1. Enrollment will continue at each of the above 3 stages while efficacy and safety data are accumulated and evaluated.

Additionally, after 5, 15, 30, and 50 participants have enrolled on each arm, respectively, and been treated for 3 cycles, cumulative safety data will be evaluated by the DRC to ensure continued study treatment is safe.

Part 2:

For Part 2, the treatment group to be studied will be dependent upon the results from Part 1. At the end of Part 1, all available data will be evaluated by the DRC to select 1 of the cusatuzumab treatment groups for further evaluation in Part 2.

The sample size for Part 2 will result in approximately 100 participants for the selected treatment group from Parts 1 and 2 combined. A formal interim analysis of the primary endpoint, CR rate, is planned during Part 2 to include 80 participants from the selected dose group, at the time when the last participant of the 80 has been treated for a minimum of 4 cycles of combination therapy. The final analysis will be based on 100 participants. A diagram of the study design is provided in Section 1.2, Figure 1.

NOTE: Part 2 of the study will not be conducted because further development of this regimen (cusatuzumab in combination with azacitidine) in patients with unfit AML will not be pursued due to the evolving treatment landscape in AML.

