2.2. Background

2.2.1. Acute myeloid leukemia

Acute myeloid leukemia (AML) is a heterogeneous disease characterized by uncontrolled clonal expansion of hematopoietic progenitor cells. As the most common form of acute leukemia, AML accounts for the largest number of annual deaths from leukemia. This poor prognosis is in part due to the fact that AML affects patients at a more advanced median age of 67 years with a third of patients diagnosed at an age of over 75 years.^{17,18} Advanced age associated with comorbidities, end-organ dysfunction, and poor performance status severely limits tolerance to intensive chemotherapy.

In addition, the biology of AML in the elderly contributes to the poor therapeutic outcome. In older patients, AML arises more frequently from an overt or unrecognized myelodysplastic syndrome (MDS), and appears to be associated with complex, monosomal, or combination karyotypes, adverse cytogenetics, as well as a multidrug resistant phenotype.¹⁵ In recent years, hypomethylating agents such as azacitidine and decitabine have emerged as one of the preferred therapies for AML patients who cannot tolerate intense induction and consolidation

chemotherapy.^{4,15} Azacitidine or decitabine monotherapy results in low response rates (10%-50%, including hematologic improvement), requires 3.5 to 4.3 months to achieve best response, and is not curative, with a median overall survival (OS) of less than 1 year.^{7,12} Thus, there is a critical need to develop targeted therapies capable of rapidly inducing a high rate of clinical response, with better tolerability and durable responses for elderly patients with AML.

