As of 15 October 2018, in the Phase 1 portion (n=12) of the ARGX-110-1601 study of cusatuzumab in combination with azacitidine in AML patients, other than expected IRRs, there were no safety signals identified other than known azacitidine toxicities. Infusion-related reactions were generally low grade; 1 subject (7.1%) was reported with a Grade 3 IRR leading to cusatuzumab discontinuation. Fifty percent of subjects (6 of 12) were reported with Grade 3 or 4 hematologic toxicities including anemia, thrombocytopenia, neutropenia, leukopenia and febrile neutropenia.

Efficacy

As of 15 October 2018, in the Phase 1 portion of the ARGX-110-1601 study (n=12), 50% of subjects had adverse risk AML and the median age was 75 years. Eight subjects (67%) achieved CR and 11 subjects (92%) demonstrated a response including CR, CRi, and partial response (PR) and 1 subject (8.3%) had stable disease. The median time to first response was 14 weeks and 3 subjects (25%) reached a first response after a single dose of cusatuzumab (prior to initiation of azacitidine therapy). The median duration of response was 5.5 months. The median event free survival was 8.1 months (range: 2 months - 17.4 months).

Pharmacokinetics

In the Phase 1 portion of study ARGX-110-1601, four dose levels (1, 3, 10 and 20 mg/kg every 2 weeks) of cusatuzumab in combination with azacitidine were administered to AML patients. Based on preliminary PK analysis, for dosing regimens of 1 and 3 mg/kg every 2 weeks, the serum drug exposures were lower after the 2nd dose compared to that of the 1st dose due to the presence of ADA. Doses of 1 or 3 mg/kg every 2 weeks resulted in peripheral C_{trough} of <50 µg/mL in AML patients. A linear PK was observed in the dose range of 10 to 20 mg/kg administered every 2 weeks with an estimated mean half-life of 200 to 262 hr (8.3-11 days). A peripheral C_{trough} >100 µg/mL was achieved with dosing regimens of 10 mg/kg and 20 mg/kg every 2 weeks for subjects with adverse risk AML.

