8.1. Efficacy Assessments

Disease assessments are based on bone marrow evaluations, peripheral blood counts, and the presence of extramedullary disease and will be conducted per the Schedule of Activities at the local laboratory (Table 1/Table 1A). Bone marrow aspirates should be performed for the disease assessment (for bone marrow blasts), for biomarker testing, and for PK. In case of a dry tap, the biopsy may also be utilized for disease assessment. Extramedullary disease evaluations may include computed tomography (CT) scans, magnetic resonance imaging (MRI), positron emission tomography (PET) scans, ultrasound, and physical examinations. See Table 2 for bone marrow biomarker sampling and Table 3 for bone marrow PK sampling. All treatment decisions will be based on local assessments. De-identified copies of the bone marrow aspirate (or biopsy)

pathology report will be sent in to the Sponsor. Transfusion status should also be collected per Schedule of Activities at the time of disease evaluations.

Participants will be assessed for disease status based on the ELN 2017 Response Criteria in AML (Table 6) at the timepoints indicated in Schedule of Activities through CR, CRi, CRh, and at the time of progressive disease. If progressive disease is suspected due to clinical indications or increased peripheral blast counts, then a bone marrow sample must be obtained to confirm progressive disease as defined in Table 6. In the case of overt leukostasis, uncontrollable coagulopathy, or new extramedullary leukemia requiring immediate action and a bone marrow sample cannot be obtained, the Sponsor must be consulted to confirm progressive disease for the participant.

Before participants discontinue the Treatment Phase due to progressive disease or relapse from CR/CRi/CRh, sites will document progressive disease or relapse as soon as possible and within 48 hours. The primary reason for discontinuation of study treatment is to be recorded in the eCRF. For all participants, the Sponsor should be informed as soon as progressive disease or relapse from CR/CRi/CRh is confirmed. Discontinuation criteria for all participants must be reviewed and confirmed by the Sponsor prior to discontinuation.

Investigator's disease assessments will be used for response in Part 1 . Overall best response across all cycles of treatment will be used to assess response rate. For an overall best response of stable disease, disease stabilization must have lasted for at least 3 months.

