9.5. Interim Analyses

For each analysis (3 stages in Part 1 and the formal interim and final analysis in Part 2), the data cutoff will be the time point when the last participant in the respective analysis has been treated for a minimum of 3 cycles (Part 1) or 4 cycles (Part 2) of the combination therapy.

NOTE: Part 2 of the study will not be conducted because further development of this regimen (cusatuzumab in combination with azacitidine) in patients with unfit AML will not be pursued due to the evolving treatment landscape in AML.

Study Part 1

Part 1 of the study consists of 3 stages of monitoring to select a dose schedule. The cumulative number of participants for each dose group at each of the 3 stages are 15, 30, and 50, respectively. At each stage, each dose group's response rate will determine independently (without formal statistical comparison to the other group) if that dose group will be stopped or continued into the next stage or into study Part 2. Only 1 dose group will be selected for Part 2. The statistical criteria for such a determination will be based on the number (and percentage) of participants in each dose group achieving CR.

The purpose of the 3-stage monitoring in Part 1 is to select, or to eliminate a dose, which will be based on the Pocock beta-spending function with an overall beta level of 10% allocated to the 3 stages with respective and cumulative sample sizes of 15 (30%), 30 (60%), and 50 (100%) participants per group. Per this approach, the statistical decision criteria and corresponding inferences are summarized in Table 7, where 2 possible outcomes resulting in a stop or continuation decision, respectively, are presented for each stage.

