The statistical criteria shown in Table 7 ensure that the false negative error rate (ie, the probability of a stopping decision, when the true CR rate is $\geq 35\%$) is $\leq 6\%$ at any stage; or equivalently, the upper limit of the 1-sided $>94\%$ confidence interval (CI) of the observed CR rate is $< 35\%$ (which means that a CR rate of 35% or greater has been statistically ruled out). It's important to control the false negative error rate at a low level when the number of participants is small to ensure that a stopping decision will not be made unless it is statistically convincing that a CR rate of $\geq 35\%$ has been ruled out. The false positive error rate (ie, the probability of a continuation decision, when the true CR rate is $\leq 20\%$) is also assessed, but controlling the false positive error rate at a low level is not of a concern, hence is not applied in this circumstance (Table 8).

Table 7: Statistical Decision Parameters for Study Part 1: Observed CR, 1-Sided Confidence Interval (CI), and Statistical Decision

	Number (%) of Observed CR	1-Sided CI Upper Bound ¹ (%)	Decision	False Negative Error ²	False Positive Error ³
Stage 1, n=15	1 (6.7)	26.7	Stop	≤4%	NA
	2 (13.3)	34.9			
	3 (20.0)	42.3	Continue to Stage 2	NA	≤50%
	4 (26.7)	49.3			
Stage 2, n=30	5 (16.7)	30.5	Stop	≤5%	NA
	6 (20.0)	34.3			
	7 (23.3)	37.9	Continue to Stage 3	NA	≤32%
	8 (26.7)	41.5			
Stage 3, n=50	11 (22.0)	32.3	Stop	≤6%	NA
	12 (24.0)	34.4			
	13 (26.0)	36.6	Continue to Part 2	NA	≤14%
	14 (28.0)	38.7			

¹ 96%, 95%, and 94% for Stage 1, 2, and 3, respectively.

² False negative error: probability of a “stop” decision, when the true CR rate is ≥35%.

³ False positive error: probability of a “continue” decision, when the true CR rate is ≤20%.

Note: All statistical inferences are based on Wilson Score statistics without continuity correction.

If the number of participants at each stage is not exactly as specified in Table 7 the Pocock beta-spending function with an overall beta level of 10% will be adjusted based on the actual number participants.

Per statistical criteria specified in Table 7, certain operating characteristics of particular interest are presented in Table 8, showing the probability of making a correct decision.

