1.2. Trial Design

The study consists of 2 sequential parts, Part 1 and Part 2. The purpose of Part 1 is to select a dose level (10 mg/kg or 20 mg/kg) based on the totality of the data, including CR rate and other efficacy endpoints, PK, biomarkers, and safety. The purpose of Part 2 is to further evaluate and confirm the efficacy and safety of the combination therapy at the selected dose of cusatuzumab.

During Part 1, participants are randomly assigned in a 1:1 ratio, with stratification by types of AML (de novo versus secondary AML) and ECOG score (0-1 versus 2), in one of the 2 treatment groups:

- Group A: Azacitidine 75 mg/m² SC or IV on Day 1 through Day 7, cusatuzumab 10 mg/kg IV on Day 3 and Day 17 of each 28-day cycle
- Group B: Azacitidine 75 mg/m² SC or IV on Day 1 through Day 7, cusatuzumab 20 mg/kg IV on Day 3 and Day 17 of each 28-day cycle

A 3-stage monitoring approach, as the statistical guidance, is utilized in Part 1 to select a dose level (see Section 1.5, Interim Analysis). The cumulative number of participants for each dose group at each of the 3 stages is 15, 30, and 50, respectively. Available data will be evaluated after the last enrolled participant has been treated for 4 cycles with the combination therapy.

Additionally, after 5 participants have enrolled on each arm and been treated for 2 cycles, cumulative safety data will be evaluated by the DRC to ensure continued study treatment is safe.

For Part 2, the treatment group to be studied will be dependent upon the results from Part 1. Approximately 100 participants are included for the selected treatment group from Parts 1 and 2 combined. A formal interim analysis of the primary endpoint, CR rate, is planned during Part 2 to include 80 participants from the selected dose group. The final analysis will be based on 100 participants.

[figure not shown]
Upon 1 dose level being selected to continue, ongoing participants who are not receiving the selected cusatuzumab dose may switch to that dose. This will be following review and approval of the selected dose by the Data Review Committee (DRC) (see below).

A diagram of the study design is provided in [Figure 1](#).

A Data Review Committee (DRC) will be established to review cumulative safety and efficacy data at planned interim time points, to ensure participants' safety, to evaluate efficacy results, and to make recommendations on dose selection, study continuation, and other study conduct related

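### The Part 1 false-negative rates in Tables 7 and 8 assume every eventual CR has been seen at a look that requires only 3 cycles, so the true error is higher by an amount the documents do not fix.

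*Protocol*

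**What the plan says.** Protocol 4.1 sets the Part 1 looks by cumulative number per dose group: "The cumulative number of participants for each dose group at each of the 3 stages are 15, 30, and 50, respectively". It fixes the data cut for each: "Response will be based on all evaluations up to the time point when the last participant is treated for a minimum of 3 cycles". Protocol 9.5 and SAP 1.5 repeat the cut as "treated for a minimum of 3 cycles (Part 1) or 4 cycles (Part 2) of the combination therapy". SAP 1.2 gives a different one for Part 1: "Available data will be evaluated after the last enrolled participant has been treated for 4 cycles with the combination therapy".

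The quantity being judged is defined in Protocol 8.1: "Overall best response across all cycles of treatment will be used to assess response rate". Marrow is evaluated at the end of Cycles 1, 3, 5 and so on (Table 1).

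On error rates, Protocol 9.5 states: "The statistical criteria shown in Table 7 ensure that the false negative error rate" is at most 6% at any stage. It adds that a stop means a CR rate of 35% or more has been statistically excluded. SAP 1.5 says the same. Table 7 (SAP Table 1) stops a dose at 2 or fewer CRs of 15, 6 or fewer of 30, or 12 or fewer of 50, with false-negative errors of at most 4%, 5% and 6%. Table 8 gives a 98.4% probability that at least one dose continues when both true rates are 35%.

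Two background figures bear on timing. For the earlier study of the combination, Protocol 2.2.2.1 reports: "The median time to first response was 14 weeks". For hypomethylating agents alone, Protocol 2.2.1 says treatment "requires 3.5 to 4.3 months to achieve best response".

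**The concern.** Three 28-day cycles are 84 days, or 12 weeks. A participant at that minimum has had two scheduled post-baseline marrow evaluations. Anyone who reaches CR later counts as a non-responder at the look, although the 35% target counts that person as a CR. The look therefore estimates something smaller than the rate it is compared with, and the bias runs towards stopping.

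The plan says the false-negative rate is the error it most wants to keep low when numbers are small, and that it deliberately leaves the false-positive rate loose. The understated error is thus the one the rule exists to control. A Stage 1 or Stage 2 stop closes a dose to enrolment. A committee using the criteria even as guidance would take a stop signal as stronger evidence than it is.

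**Working it through.** **1. Reproduce the printed figures.** Inputs: n = 15, 30, 50; stop at 2, 6, 12 or fewer CRs (Table 7); true CR rate 0.35 or 0.20 (Protocol 9.1).

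Table 7's false-negative column comes from the normal score tail, z = (s − 0.35n)/√(n × 0.35 × 0.65). At Stage 1, z = (2 − 5.25)/1.847 = −1.76, giving 3.9%. Stages 2 and 3 give 4.2% and 5.1%. These match the printed bounds of 4%, 5% and 6%. The exact binomial tails are slightly higher. At Stage 1, 0.65^15 + 15(0.35)(0.65^14) + 105(0.35²)(0.65^13) = 0.0016 + 0.0126 + 0.0476 = 6.2%. Stages 2 and 3 are 5.9% and 6.6%.

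An exact three-stage recursion at 0.35 gives wrong stops of 6.17% + 3.35% + 3.12%, or 12.65% after rounding, per dose. For two independent doses, 1 − 0.1265² = 98.4%, which is Table 8's first cell. With a stop probability of 84.99% at a true 20%, the other cells are (1 − 0.1265) × 0.8499 = 74.2% (printed 74.3%) and 0.8499² = 72.2% (printed 72.1%). Table 8 therefore uses the full CR rate at every look.

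The fair baseline for what follows is the exact one, 6.2% at Stage 1 and 12.6% cumulatively. The difference between 6.2% and the printed 4% is a separate matter of approximation.

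**2. Allow for CRs not yet seen.** Let f be the share of eventual CRs visible at the look, and replace 0.35 by 0.35f. At f = 0.80 the rate is 0.28. Stage 1 becomes 0.72^15 + 15(0.28)(0.72^14) + 105(0.28²)(0.72^13) = 0.0072 + 0.0423 + 0.1150 = 16.5%.

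| f, same at every look | Stage 1 wrong stop | Cumulative wrong stop | Table 8, first cell |
|---|---|---|---|
| 1.00 | 6.2% | 12.6% | 98.4% |
| 0.90 | 10.3% | 24.1% | 94.2% |
| 0.80 | 16.5% | 41.1% | 83.1% |

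**3. Let visibility vary with entry time.** Earlier entrants have more follow-up, so f rises from Stage 1 to Stage 3. The documents give neither a time-to-CR distribution nor an accrual rate, so the following are assumptions: even accrual; time to CR exponential or log-normal (log-SD 0.5); CR documented at weeks 4, 12, 20 and so on; each look 12 weeks after entry of the 15th, 30th or 50th participant. Ranges span the two distributions.

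| Assumed median time to CR | Accrual per arm per 4 weeks | Visible at Stage 1 | Stage 1 wrong stop | Cumulative wrong stop |
|---|---|---|---|---|
| 8 weeks | 1 | 91–97% | 7–10% | 14–18% |
| 12 weeks | 2 | 71–81% | 15–24% | 25–37% |
| 12 weeks | 4 | 59–66% | 29–38% | 41–58% |

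In the middle row, visibility reaches 89–94% by Stage 3.

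**The case against.** The size depends on inputs the documents do not contain. The 14-week figure is a median time to first response (CR, CRi or PR) from 12 subjects. It includes a 14-day monotherapy cycle, so it is about 12 weeks from the start of azacitidine. Half of those subjects received 1 or 3 mg/kg, which this trial does not study. Within a patient CR cannot precede first response, but that does not order the medians: 11 subjects responded and 8 reached CR, so if the others responded late, median time to CR could be shorter than 14 weeks. The hypomethylating-agent figure is for monotherapy, and one of its two citations is a trial in higher-risk MDS. Neither is a time to CR on this regimen. All of this stands, and it is why the size is given as a range with a favourable end close to the baseline.

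A reader might take 41% as the real error. The documents do not support that: it needs 80% visibility at all three looks, whereas staggered entry makes visibility rise. Nor does the 4-cycle cut in Part 2 show that 3 cycles is too short, because evaluations fall at the end of odd cycles and a fourth cycle adds no scheduled evaluation for the last participant.

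The consequences are also softened. The criteria are guidance, weighed with the totality of the data. Under Protocol 4.1, if one dose stops at Stage 1 or 2 the other goes directly to Part 2, a rule Table 8 ignores. With it, the chance that at least one of two 35% doses continues is 99.4% at full visibility and still 94.2% at 80%. Losing both doses is therefore much less likely than losing a particular one.

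None of this restores the printed per-dose error rates. Those hold only if every eventual CR has been seen.

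**Conclusion.** The point holds as a fault in the stated operating characteristics. Tables 7 and 8 make no allowance for CRs after the cut, the direction of the error is certain if any such CRs occur, and the claim that the criteria guarantee a false-negative rate of at most 6% and exclude a 35% CR rate is not met at a 3-cycle cut. Against exact baselines of 6.2% at Stage 1 and 12.6% over three looks, the cumulative wrong stop of a true 35% dose is about 14% to 58%. That range rests on assumed median times to CR of 8 to 12 weeks and assumed accrual of 1 to 4 per arm per 4 weeks. The documents cannot narrow it.

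A reader might infer that an effective dose was in fact wrongly stopped. The documents give no ground for that: SAP 1.6 says all three stages were completed, Part 2 was not pursued, and Part 1 is to be reported descriptively. The correction matters for how the stage results are interpreted and reported.

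**What to change.** In Protocol 9.5 and SAP 1.5:

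- State the assumed time-to-CR distribution and accrual rate.
- Restate the false-negative column of Table 7 (SAP Table 1) and the Table 8 probabilities for the cut actually used. At the least, state that the printed figures hold only if all CRs have been observed at the look.
- Replace the wording that the criteria guarantee the error rate and that a 35% CR rate has been excluded with wording that matches the restated figures.
- Reconcile the 4-cycle Part 1 cut in SAP 1.2 with the 3-cycle cut in SAP 1.5.

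The cost is a recalculation and some text, and the stated error rates become less favourable.

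Two larger changes should not be adopted without showing their price. Cut-offs lowered to suit 80% visibility (stop at 1 or fewer of 15, 4 of 30, 8 of 50) raise the chance of continuing a true 20% dose from 3.7% to 33% at 80% visibility, and from 15% to 59% at full visibility. Counting participants only once their CR status is settled admits early CRs and early failures first, so inclusion would depend on outcome.
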